- 24. Women who are pregnant or breast feeding or adults of reproductive potential not employing an effective method of birth control. Double barrier contraceptives must be used through the trial by both sexes. Oral, implantable, or injectable contraceptives may be affected by cytochrome P450 interactions, and are therefore not considered effective for this study. Women of child-bearing potential, defined as sexually mature women who have not undergone a hysterectomy or who have not been naturally postmenopausal for at least 12 consecutive months (ie, who has had menses any time in the preceding 12 consecutive months), must have a negative serum pregnancy test ≤ 72 hours prior to initiating treatment.
 - ♦♦ Women are considered post-menopausal and not of child bearing potential if they have had 12 months of natural (spontaneous) amenorrhea with an appropriate clinical profile (eg, age appropriate, history of vasomotor symptoms) or six months of spontaneous amenorrhea with serum FSH levels > 40 mIU/mL (for US only: and estradiol < 20 pg/mL) or have had surgical bilateral oophorectomy (with or without hysterectomy) at least six weeks ago. In the case of oophorectomy alone, only when the reproductive status of the woman has been confirmed by follow up hormone level assessment is she considered not of child bearing potential.
 - •• Women of child-bearing potential, defined as all women physiologically capable of becoming pregnant, must use highly effective contraception during the study and through 20 months after the final dose of study treatment. For males with partners with childbearing potential, highly effective contraception is required for 6 months. The highly effective contraception is defined as either:
- I. True abstinence: When this is in line with the preferred and usual lifestyle of the subject. Periodic abstinence (eg, calendar, ovulation, symptothermal, post-ovulation methods) and withdrawal are not acceptable methods of contraception.
- II. Sterilization: have had surgical bilateral oophorectomy (with or without hysterectomy) or tubal ligation at least six weeks ago. In case of oophorectomy alone, only when the reproductive status of the woman has been confirmed by follow up hormone level assessment.
- III. Male partner sterilization (with the appropriate post-vasectomy documentation of the absence of sperm in the ejaculate). For female subjects on the study, the vasectomised male partner should be the sole partner for that patient.

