- IV. Use of a combination of any two of the following (a+b):
 - a. Placement of an intrauterine device (IUD) or intrauterine system (IUS)
 - b. Barrier methods of contraception: Condom or Occlusive cap (diaphragm or cervical/vault caps) with spermicidal foam/gel/film/cream/vaginal suppository

- •• Oral contraception, injected or implanted hormonal methods are not allowed as buparlisib potentially decreases the effectiveness of hormonal contraceptives.
- ◆◆ Fertile males, must use highly effective (double barrier) methods of contraception (eg, spermicidal gel plus condom) for the entire duration of the study, and continuing using contraception and refrain from fathering a child for 6 months following the study drug. A condom is required to be used also by vasectomized men as well as during intercourse with a male partner in order to prevent delivery of the study treatment via seminal fluid. Female partner of male study subject should use highly effective contraception during dosing of any study agent and for 16 weeks after final dose of study therapy.

Note: Hormonal contraception methods (eg, oral, injected, implanted) are not allowed as it cannot be ruled out that the study drug decreases the effectiveness of hormonal contraception.

Note: Woman are considered post-menopausal and not child bearing potential if they have had 12 months of natural (spontaneous) amenorrhea with an appropriate clinical profile (eg, age appropriate, history of vasomotor symptoms) or six months of spontaneous amenorrhea with serum FSH levels > 40 mIU/ mL and estradiol < 20 pg/mL or have had surgical bilateral oophorectomy (with or without hysterectomy) at least six weeks ago. In the case of oophorectomy alone, only when the reproductive status of the woman has been confirmed by follow up hormone level assessment is she considered not of child bearing potential

- 25. Known diagnosis of human immunodeficiency virus (HIV) infection, Hepatitis B or Hepatitis C
- 26. History of another malignancy within 3 years, except cured basal cell carcinoma of the skin or excised carcinoma in situ of the cervix
- 27. Patient is unable or unwilling to abide by the study protocol or cooperate fully with the investigator

4 Treatments

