All adverse events will be attributed to LB therapy unless they can be clearly attributed to progression or to another clearly identified etiology by the investigator. Adverse events will be graded according to the National Cancer Institute Common Terminology Criteria for Adverse Events Version 3.0.

Intolerable toxicities are defined as new (not present at baseline) Grade 3 or 4 adverse events deemed to be related to LB therapy that are life threatening or irreversible, and when (in the opinion of the investigator) the risks outweighs the benefit of continued treatment.

Women of childbearing potential will be required to have a negative serum pregnancy test at screening, urine pregnancy test on Day 1 and every 4 weeks while on study. Women of childbearing potential or male patients with female partners of childbearing potential are required to use a highly reliable method of contraception, and for 12 weeks after discontinuation of LB therapy. Patients must agree not to donate bodily fluids for 12 months after discontinuation of LB therapy.

Safety assessments will consist of monitoring and recording all adverse events and serious adverse events, the regular monitoring of hematology, blood chemistry and urine values, regular measurement of vital signs and the performance of physical examinations. These assessments should be performed within ±2 days of the scheduled day of assessment except for adverse events that will be evaluated continuously through the study. Safety and tolerability will be assessed according to the NIH/NCI CTC (http://ctep.cancer.gov/protocolDevelopment/electronic applications/ctc.htm#ctc 40).

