 14. Women of child-bearing potential, defined as all women physiologically capable of becoming pregnant, including women whose career, lifestyle, or sexual orientation precludes intercourse with a male partner and women whose partners have been sterilized by vasectomy or other means, UNLESS they are using two birth control methods. The two methods can be a double barrier method or a barrier method plus a hormonal method. Adequate barrier methods of contraception include: Diaphragm, condom (by the partner), intrauterine device (copper or hormonal), sponge or spermicide. Hormonal contraceptives include any marketed contraceptive agent that includes an estrogen and/or a progestational agent. Reliable contraception should be maintained throughout the study and for 3 months after study drug discontinuation. 	

15. Uncontrolled medical medical problems including acute or chronic liver disease, renal disease or pancreatitis, diarrhea >CTCAE grade 2, active cardiac disease, uncontrolled diabetes, chronic steroids or other immunosuppressive agents		
16. Patients who have taken herbal medications and certain fruits within 7 days prior to starting study drug. Herbal medications include, but are not limited to St. John's Wort, Kava, ephedra (ma huang), dehydroepiandrosterone (DHEA), gingko biloba, yohimbe, saw palmetto, and ginseng. Fruits include the CYP3A inhibitors Seville oranges, grapefruit, pummelos, or exotic citrus fruits.		
17. Patients who are currently treated with drugs known to be moderate and strong inhibitors or inducers of isoenzyme CYP3A, and the treatment cannot be discontinued or switched to a different medication prior to starting study drug. Please refer to Table 15 for a list of prohibited inhibitors and inducers of CYP3A (Please note that co-treatment with weak inhibitors of CYP3A is allowed).		
18. Patients who have received any continuous or intermittent small molecule therapeutics (excluding monoclonal antibodies) ≤ 5 effective half lives prior to starting study drug or who have not recovered from side effects of such therapy		
19. Use of statin drugs or other medications known to associate with rhabdomyolysis. These drugs must be discontinued at enrollment		

20. Patients who have received wide field radiotherapy ≤ 4 weeks or limited field radiation for palliation ≤ 2 weeks prior to starting study drug or who have not recovered from side effects of such therapy	

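### Post-treatment contraception periods conflict between exclusion 24, section 4.3.3 and Appendix B, and the checklist accepts a hormonal method that exclusion 24 rejects

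*Combined protocol and SAP*

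**What the plan says.** Three places set the period after the last dose.

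- **Section 3.2.2.2, exclusion 24.** Women of childbearing potential "must use highly effective contraception during the study and through 20 months after the final dose of study treatment". For male patients the period is given twice: "For males with partners with childbearing potential, highly effective contraception is required for 6 months", and fertile men must "refrain from fathering a child for 6 months following the study drug".
- **Section 4.3.3.** One rule covers women who could become pregnant and men whose partners could. They "are required to use a highly reliable method of contraception, and for 12 weeks after discontinuation of LB therapy".
- **Appendix B, exclusion item 14 (women only).** "Reliable contraception should be maintained throughout the study and for 3 months after study drug discontinuation".

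The same places differ on method. Appendix B item 14 requires two methods and adds: "The two methods can be a double barrier method or a barrier method plus a hormonal method". Exclusion 24 says: "Oral, implantable, or injectable contraceptives may be affected by cytochrome P450 interactions, and are therefore not considered effective for this study". It also says: "Oral contraception, injected or implanted hormonal methods are not allowed as buparlisib potentially decreases the effectiveness of hormonal contraceptives". Section 4.2.3.1 repeats that hormonal contraceptives are not considered effective in this study.

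Section 1.4.4 says that sonidegib has been found to be teratogenic.

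**The concern.** These rules apply to the same people and run from the same starting point, the end of study treatment. As statements of how long contraception is required, they cannot all be right. The document has no rule saying which section prevails.

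Two features make this more than untidy drafting. Appendix B is a working form that ends in a signed statement that the subject is eligible or ineligible, so its wording may be applied directly at enrolment. And routine adverse event follow-up ends 28 to 30 days after the last dose (sections 4.1 and 4.1.1), before even the shortest contraception period has run. A patient given the shorter period might have no later study contact at which it is corrected.

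At stake is fetal exposure to a drug that the protocol calls teratogenic, given with buparlisib. Buparlisib is described as having a genotoxic potential, probably aneugenic. It also caused testicular toxicity that had not fully reversed after four treatment-free weeks in rats at the highest dose (sections 1.5.1.1 and 1.5.1.2.2).

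**Working it through.** The check compares texts, with unit conversion at 1 month = 30.44 days. The plan gives no derived figure to reproduce.

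| Group | Exclusion 24 | Section 4.3.3 | Appendix B item 14 |
|---|---|---|---|
| Women of childbearing potential | 20 months | 12 weeks | 3 months |
| Male patients | 6 months | 12 weeks | no item |
| Hormonal method | not accepted | not addressed | accepted with a barrier |

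**Women**
- Exclusion 24: 20 × 30.44 = 608.8 days.
- Section 4.3.3: 12 × 7 = 84 days. Gap 608.8 − 84 = 524.8 days, and 524.8 / 30.44 = 17.2 months. Ratio 608.8 / 84 = 7.2.
- Appendix B: 3 × 30.44 = 91.3 days. Gap 608.8 − 91.3 = 517.5 days, and 517.5 / 30.44 = 17.0 months. Ratio 608.8 / 91.3 = 6.7.

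The 84 and 91 days differ by about a week, so there are in effect two competing periods for women, not three.

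**Male patients**
- Exclusion 24: 6 × 30.44 = 182.6 days.
- Section 4.3.3: 84 days. Gap 182.6 − 84 = 98.6 days, and 98.6 / 7 = 14.1 weeks. Ratio 182.6 / 84 = 2.2.

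Appendix B has no contraception item for men, so the male conflict is between exclusion 24 and 4.3.3 only.

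**Method.** Take a woman who uses a barrier plus an oral, injected or implanted hormonal method. Under Appendix B item 14 she has two acceptable methods and is not excluded. Under exclusion 24 the hormonal method is not allowed and does not count. If she meets none of the other options there, she is excluded. The form and the protocol give opposite answers for the same woman.

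**Can the pharmacokinetics settle which period is right?** Sonidegib half-lives elapsed in 84 days:
- 84 / 10 = 8.4, at the median terminal half-life after a single dose in healthy subjects (section 1.4.7.2.1);
- 84 / 11 = 7.6, at the median effective half-life in patients (section 1.4.7.2.1);
- 84 / 14 = 6.0, at the top of the 1 to 14 day range (section 1.4.7.1).

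On these figures little drug would remain at 12 weeks, which favours the shorter period. However, section 1.4.7.1 says that an accurate terminal half-life could not be obtained in patients by a non-compartmental approach, and no section links any half-life to any contraception period. The figures therefore neither confirm 12 weeks nor explain 20 months.

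**The case against.** The strongest reply is that exclusion 24 governs anyway. Section 3.2.2 requires every patient to meet all the criteria, with the investigator or a designee reviewing the results before enrolment. The shorter periods can be read as minimums, so a patient who follows exclusion 24 satisfies all three texts. The study is at a single center, and what patients are told depends on consent text that was not available for this review. That reply limits the consequence but leaves the conflict. Nothing in 4.3.3 or Appendix B points back to exclusion 24, and Appendix B is the form that is signed.

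Four stronger readings are tempting and are not supported.

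- A reader might infer that the site would tell women to stop contraception 17 months early. The documents show only that staff could apply a shorter period.
- A reader might infer that the protocol calls a barrier plus a hormonal method ineffective as a pair. It rejects the hormonal component and says nothing against the barrier. The defect is that the checklist counts a disallowed second method.
- A reader might infer from Table 19 that the regular pregnancy tests are not required, or will be missed. The table's row is a serum test to be done when clinically indicated, but sections 4.3.3 and 4.3.5.2 require testing every 4 weeks or monthly, and that duty stands. The table was also damaged in text extraction. This is a minor note.
- A reader might infer that 12 weeks is unsafe. The half-life figures suggest that the added risk may be small.

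The 16 weeks in exclusion 24 for female partners of male patients has no competing value elsewhere and is not part of this point.

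**Conclusion.** The conflict stands in the current text. For women of childbearing potential, exclusion 24 exceeds 4.3.3 and Appendix B by about 17 months (6.7 to 7.2 times as long). For male patients it exceeds 4.3.3 by about 14 weeks (2.2 times as long). Separately, the signed checklist can pass a woman whom exclusion 24 excludes, because it counts a hormonal second method.

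The conclusion rests on reading all three texts as current requirements for the same people, and on 30.44 days per month. It does not rest on 20 months being the right period, since the documents give no reason for any of them. How many of the 24 planned patients are women of childbearing potential, or men with such partners, is not stated, so the number affected is unknown. The point concerns consistency and participant safety. It touches no endpoint, sample size or other statistical figure. It should be corrected, but it does not call the design into question.

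**What to change.** Unless the sponsor confirms other values, take exclusion 24 as the reference, because it is the more protective text.

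1. **Section 4.3.3:** replace 12 weeks with 20 months for women of childbearing potential and 6 months for male patients.
2. **Appendix B item 14:** replace 3 months with 20 months. Delete the alternative that pairs a barrier with a hormonal method, and the sentence defining hormonal contraceptives. Refer to exclusion 24 for acceptable methods.
3. **Appendix B:** add a short line for male patients giving 6 months.
4. **Minor, Table 19:** make the pregnancy-test row match the 4-weekly test that 4.3.3 and 4.3.5.2 already require, and keep the when-indicated wording for extra tests only.

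While making item 2, the sponsor should check that the list in exclusion 24 reads consistently. It first says that double barrier contraception must be used, then accepts abstinence or sterilization.

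The cost is a wording amendment, one new checklist line and one table row. The longer periods and the hormonal restriction are already in exclusion 24, and the regular tests are already required, so a site that follows those texts takes on no new duty. If the sponsor prefers a shorter period, one sentence of justification and the same value in all three places would resolve the conflict equally well.

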4.3.4 Treatment compliance

Records of study medication used, dosages administered, and intervals between visits will be recorded during the study. Drug accountability will be noted and patients will be asked to return all unused study medication.

4.3.4.1 Adverse events

Information about all adverse events, whether volunteered by the subject, discovered by investigator questioning, or detected through physical examination, laboratory test or other means, will be collected and recorded and followed as appropriate.

An adverse event is the appearance or worsening of any undesirable sign, symptom, or medical condition occurring after starting the study drug even if the event is not considered to be related to study drug. Medical conditions/diseases present before starting

study drug are only considered adverse events if they worsen after starting study drug. Abnormal laboratory values or test results constitute adverse events only if they induce clinical signs or symptoms, are considered clinically significant, or require therapy.

The occurrence of adverse events should be sought by non-directive questioning of the patient at each visit during the study. Adverse events also may be detected when they are volunteered by the patient during or between visits or through physical examination, laboratory test, or other assessments. As far as possible, each adverse event should be evaluated to determine:

- 1. the severity grade (mild, moderate, severe) or (Grade 1-4)
- 2. its relationship to the study drug(s) (suspected/not suspected)
- 3. its duration (start and end dates or if continuing at final exam)
- 4. action taken (no action taken; study drug dosage adjusted/temporarily interrupted; study drug permanently discontinued due to this adverse event; concomitant medication taken; non-drug therapy given; hospitalization/prolonged hospitalization)
- 5. whether it constitutes a serious adverse event (SAE)

All adverse events should be treated appropriately. Such treatment may include changes in study drug treatment including possible interruption or discontinuation, starting or stopping concomitant treatments, changes in the frequency or nature of assessments, hospitalization, or any other medically required intervention. Once an adverse event is detected, it should be followed until its resolution, and assessment should be made at each visit (or more frequently, if necessary) of any changes in severity, the suspected relationship to the study drug, the interventions required to treat it, and the outcome.

Information about common side effects already known about the investigational drug can be found in the Investigators' Brochure. This information should be included in the patient informed consent and should be discussed with the patient during the study as needed.

4.3.4.2 Serious adverse events

A serious adverse event is an undesirable sign, symptom or medical condition which:

- ◆ is fatal or life-threatening
- •• results in persistent or significant disability/incapacity
- ◆◆ constitutes a congenital anomaly/birth defect
- •• requires inpatient hospitalization or prolongation of existing hospitalization, unless hospitalization is for:
- •• routine treatment or monitoring of the studied indication, not associated with any deterioration in condition (specify what this includes)
- •• elective or pre-planned treatment for a pre-existing condition that is unrelated to the indication under study and has not worsened since the start of study drug
- ◆◆ treatment on an emergency outpatient basis for an event not fulfilling any of the definitions of a SAE given above and not resulting in hospital admission
- •• social reasons and respite care in the absence of any deterioration in the patient's general condition
- •• is medically significant, ie, defined as an event that jeopardizes the patient or may require medical or surgical intervention to prevent one of the outcomes listed above

To ensure patient safety, every SAE, regardless of suspected causality, occurring

- ◆◆ after the patient has provided informed consent and until 4 weeks after the patient has stopped study treatment/participation
- ♦♦ after the patient begins taking study drug and until 4 weeks after the patient has stopped study treatment
- ◆◆ after protocol-specified procedures begin (eg, placebo run-in, washout period, double-blind treatment, etc.) and until 4 weeks after the patient has stopped study treatment
- ** after the start of any period in which the study protocol interferes with the standard medical treatment given to a patient (eg, treatment withdrawal during washout period, change in treatment to a fixed dose of concomitant medication) and until 4 weeks after the patient has stopped study treatment must be reported to Novartis within 24 hours of learning of its occurrence. Any SAEs experienced after this 4-week period should only be reported to Novartis if the investigator suspects a causal relationship to the study drug. Recurrent episodes, complications, or progression of the initial SAE must be reported as follow-up to the original episode within 24 hours of the investigator receiving the follow-up information. An SAE occurring at a different time interval or otherwise considered completely unrelated to a previously reported one should be reported separately as a new event.

The investigator must assess and record the relationship of each SAE to each specific study drug (if there is more than one study drug), complete the SAE Report in English, and send the completed, signed form by [contact]) within 24 hours to the Novartis Drug Safety and Epidemiology Department. The original copy of the SAE

Report and the fax confirmation sheet must be kept within the Trial Master File at the study site.

Follow-up information is sent to the same person to whom the original SAE Report Form was sent, using a new SAE Report Form stating that this is a follow-up to the previously reported SAE and giving the date of the original report. Each re-occurrence, complication, or progression of the original event should be reported as a follow-up to that event regardless of when it occurs. The follow-up information should describe whether the event has resolved or continues, if and how it was treated, whether the blind was broken or not (if applicable), and whether the patient continued or withdrew from study participation. If the SAE is not previously documented in the Investigator's Brochure or Package Insert (new occurrence) and is thought to be related to the Novartis study drug, a Drug Safety and Epidemiology Department associate may urgently require further information from the investigator for Health Authority reporting. Novartis may need to issue an Investigator Notification (IN), to inform all investigators involved in any study with the same drug that this SAE has been reported.

Suspected Unexpected Serious Adverse Reactions (SUSARs) will be collected and reported to the competent authorities and relevant ethics committees in accordance with Directive 2001/20/EC or as per national regulatory requirements in participating countries.

